STATISTICAL CONSIDERATIONS	
To answer the primary objective we will calculate the sensitivity and specificity of the intraoperative findings on whether the lymph node is fluorescent (ie, presence of panitumumab-IRDye800) to the histopathological (gold standard) status of the lymph nodes.
 
Analysis for the secondary objective: We will determine if panitumumab-IRDye800 can identify sentinel nodes with the same accuracy as Lymphoseek. Similar to the primary analysis, we will calculate the specificity and sensitivity of Lymphoseek for metastatic lymph node identification, using histology as the gold standard, and compare these to the fluorescence imaging-based results. Since false negatives are of particular concern, we will calculate the diagnostic odds ratio to better understand the odds of obtaining a false negative using panitumumab-IRDye800 relative to the odds of obtaining a false negative using Lymphoseek-based sentinel node biopsy.

STUDY SCHEME

[figure not shown]

Figure 1. Schematic overview of the clinical trial in which we will directly compare panitumumab-IRDye800 to the reference standards sentinel node biopsy and neck dissection. Key steps of the clinical study are mentioned.

LIST OF ABBREVIATIONS AND DEFINITION OF TERMS

^{99m} Tc	Technetium-99m
AE	Adverse Event
BID	Twice Daily
BSA	Body Surface Area
CBC	Complete Blood Count
CI	Confidence Interval
CMAX	Maximum Concentration of Drug
CNS	Central Nervous System
CRF	Case Report/Record Form
CT	Computed Tomography
CTCAE	Common Terminology Criteria for Adverse Events
DLT	Dose-Limiting Toxicity
DSMC	Data Safety Monitoring Committee
ECG	Electrocardiogram
ECOG	The Eastern Cooperative Oncology Group
EGFR	Epidermal Growth Factor Receptor
eLND	Extensive Lymph Node Dissection
FDA	Food and Drug Administration
GMP	Good Manufacturing Practice
Hgb	Hemoglobin
HNSCC	Head and Neck Squamous Cell Carcinoma
HTN	Hypertension
ICG	Indocyanine green
ILD	Interstitial Lung Disease
IND	Investigational New Drug
IRB	Institutional Review Board
IV	Intravenous
LLN	Lower Limit of Normal
LN	Lymph Node
MTD	Maximum Tolerated Dose
NIR	Near-Infrared
NHS	N-hydroxysuccinimide
PAI	Photoacoustic imaging
PLT	Platelet
ROI	Region of Interest
SAE	Serious Adverse Event
SN	Sentinel Node
SNB	Sentinel Node Biopsy
SNR	Signal to Noise Ratio
SPECT	Single Photon Emission Computed Tomography
TBR	Tumor to Background Ratio
ULN	Upper Limit of Normal
UNK	Unknown
WBC	White Blood Cell
WHO	World Health Organization

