3. PARTICIPANT SELECTION AND ENROLLMENT PROCEDURES

3.1 Inclusion Criteria

- a. Biopsy confirmed diagnosis of squamous cell carcinoma of the head and neck
- b. Subjects with recurrent disease or a new primary will be allowed
- c. Planned standard of care surgery with curative intent for squamous cell carcinoma
- d. *** SNB only cohort:** Subjects diagnosed with a T1-T2 stage tumor, any subsite within the head and neck that is amenable to local sentinel node tracer injection and are scheduled to undergo surgical resection of the tumor, including a sentinel node biopsy
- e. *** Neck dissection only cohort:** Subjects diagnosed with any T stage, any subsite within the head and neck that are scheduled to undergo surgical resection, including a (modified) neck dissection
- f. Age \geq 19 years
- g. Karnofsky performance status of at least 70% or ECOG/Zubrod level 1
- h. Have acceptable hematologic status, coagulation status, kidney function, and liver function including the following clinical results:
 - i. Hemoglobin \geq 9 gm/dL
 - ii. White blood cell count $>$ 3000/mm³
 - iii. Platelet count \geq 100,000/mm³
 - iv. Serum creatinine \leq 1.5 times upper reference range

**Only one criterion to be checked for each participant – either “d” or “e”.*

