4. TREATMENT PLAN

4.1 Treatment Schedule

Subjects will receive intravenous panitumumab-IRDye800 (50 mg) 1 to 5 days prior to surgery. Then on the day before surgery, subjects in Cohort 1 will receive a local injection with 2 mCi Lymphoseek followed by lymphoscintigraphy and SPECT/CT imaging to determine the number and location of LNs. In the operation theatre, using a combination of fluorescence imaging and radio-tracing, the LNs of the neck will be evaluated and scored (Section 2.4, Figure 1).

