4.5 Surgical Imaging

Lymphadenectomy specimen assessment. Please see Section 2.4 for more detail. The neck will be imaged using near-infrared fluorescence and white light optical imaging systems and gamma tracing will be performed (Cohort 1 only). Imaging and tracing will be performed prior to lymphadenectomy, and after lymphadenectomy. Subsequently, the lymphadenectomy specimens will be imaged on a 'back table' prior to sending the specimens to pathology. The number and location of the fluorescent, and/or radioactive LNs will be documented.

The imaging information obtained will not be used for diagnosis or any other medical decision-making. Added surgical time for these images is expected to be minimal since these the images can be recorded for later review as still and video images. Once the specimens have been delivered to pathology, additional imaging will be performed as described above in Section 2.4.

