12.1.2. Secondary Objective and Endpoint

The **secondary objective** of the study is to determine if panitumumab-IRDye800 can identify LNs with the same efficiency as Lymphoseek.

The **secondary endpoint** is: The number and location of Lymphoseek positive LNs that are also tumor-positive at (histo-)pathology.

To answer the secondary objective: We will determine if the LN tracer Lymphoseek can identify metastatic disease in regional neck LNs of subjects with HNSCC. Similar to the primary analysis, we will calculate the specificity and sensitivity of Lymphoseek for metastatic LN identification, using histology as the gold standard, and compare these to neck dissection with Durkalski's test. Since false negatives are of particular concern, we will calculate the odds of obtaining a false negative using panitumumab-IRDye800 relative to the odds of obtaining a false negative using Lymphoseek-based SNB.

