12.1.3. Sample Size Justification and Power Considerations

We expect to enroll 10 T1/T2 node-negative subjects and 10 subjects with T1-4 and LN metastasis. Based on the data on LN collection from our current IRB-35064 study, we expect that 50% of subjects will undergo a bilateral neck dissection, meaning we would have a total of 30 necks. Assuming an average of 20 LN harvested per neck we would have a total of 600 LNs. Based on previous findings from our IRB-35064 study, we expect approximately 30-40% of subjects (6 to 8 of 20) will have metastatic LNs with an overall prevalence of 5 to 10% of the total number of harvested LNs (30 to 60 of 600) being tumor-positive.

Since this is a Phase 2 study, power considerations are limited but even so, we have excellent power to detect differences in specificity. Although we will use Durkalski's test to compare sensitivities and specificities, we estimated power by first determining the effective sample size (ESS), adjusting for the correlation of LNs within person, and then estimated power using McNemar's test on this ESS. We assumed an intra-class correlation of 0.005, yielding an effective sample size of 524 LNs. With an effective sample size of 524, a prevalence of 7.5%, a significance level of 0.05, and a 0.25 proportion of discordant pairs, we have greater than 99% power to detect a 0.1 difference in specificities, assuming the lower specificity is 0.8. Similarly, we have greater than 78% power to detect a 0.2 difference in sensitivity with the one-sided McNemar test. This assumes the proportion of discordant pairs is 0.25 and the lower sensitivity is 0.75.

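### The >99% and >78% power figures need 600 nodes each read by two tests, but only the 10 sentinel-node-only subjects receive the second tracer

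*Combined protocol and SAP*

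**What the plan says.** Section 12.1.3 plans 10 node-negative T1/T2 subjects and "10 subjects with T1-4 and LN metastasis". It expects half of all subjects to have bilateral neck dissection, hence 30 necks. "Assuming an average of 20 LN harvested per neck we would have a total of 600 LNs". With an intra-class correlation of 0.005 this becomes an effective sample size of 524. McNemar's test with a 0.25 proportion of discordant pairs then gives more than 99% power for a 0.1 difference in specificity (lower value 0.8). For sensitivity (lower value 0.75): "Similarly, we have greater than 78% power to detect a 0.2 difference in sensitivity with the one-sided McNemar test".

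Section 12.1.3 does not say which two tests form the pair, and two other places disagree. The synopsis would estimate Lymphoseek sensitivity and specificity "using histology as the gold standard, and compare these to the fluorescence imaging-based results". Section 12.1.2 would do so "using histology as the gold standard, and compare these to neck dissection".

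On who gets what:

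- Table 1 (section 2.4.2) lists no Lymphoseek for Cohort 2.
- Section 4.1: "subjects in Cohort 1 will receive a local injection with 2 mCi Lymphoseek followed by lymphoscintigraphy and SPECT/CT imaging".
- Section 4.5 limits gamma tracing to Cohort 1.
- Section 3.1 has separate criteria for a sentinel-node-biopsy-only cohort and a neck-dissection-only cohort: "Only one criterion to be checked for each participant".
- Section 2.4.3.3 has Cohort 1 nodes located with the gamma probe and removed until none is radioactive. A completion neck dissection is described only for the cN+ subjects.

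**The concern.** McNemar power depends on the number of nodes that carry both test results. The calculation uses every node from all 20 subjects, as if all were dissected and all had both results. In the design as described, dissection and the second tracer fall in different cohorts: Cohort 2 has the high node yield and no Lymphoseek, while Cohort 1 has Lymphoseek and a sentinel-node yield.

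Section 12.1.3 is the only justification offered for 20 subjects. If its power belongs to a comparison the cohorts cannot produce, the sample size has no stated basis, and the aim of showing the same accuracy as Lymphoseek is given weight it does not have. What 20 subjects can deliver, an estimate of fluorescence sensitivity and specificity against histology, has no stated expected precision.

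**Working it through.** **Inputs (section 12.1.3).** 20 subjects; 30 necks; 20 nodes per neck; ICC 0.005; prevalence 7.5% (range 5 to 10%); alpha 0.05; discordance 0.25; specificity 0.8 vs 0.9; sensitivity 0.75 vs 0.95, one-sided.

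**Step 1: reproduce the plan.**
- Nodes per subject: 600/20 = 30. Design effect: 1 + (30 − 1) × 0.005 = 1.145. Effective size: 600/1.145 = 524.
- Positive nodes: 524 × 0.075 = 39.3, taken as 40. Negative nodes: 524 × 0.925 = 484.7, taken as 485.
- Discordant cells. Sensitivity: sum 0.25 and difference 0.20 give 0.225 and 0.025. Specificity: sum 0.25 and difference 0.10 give 0.175 and 0.075.
- McNemar power, averaged over the number of discordant pairs: sensitivity at n = 40, exact one-sided, 78.1%; specificity at n = 485, exact two-sided, 99.3%.

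Both stated figures follow from the stated inputs.

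**Step 2: which nodes can be paired?** The assumed better test has specificity 0.9 and sensitivity 0.95. It cannot be histology, which as the reference would score 1.0. Neck dissection gives no node-level call apart from pathology, and no subject is scheduled for both Lymphoseek and neck dissection. That leaves fluorescence against Lymphoseek, in Cohort 1.

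**Step 3: the most generous case.** Treat Cohort 1 as fully dissected: 10 subjects, 15 necks × 20 = 300 nodes, 300/1.145 = 262 effective. All other inputs are unchanged.

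| Prevalence | Positive nodes | Sensitivity power, one-sided: exact / asymptotic | Negative nodes | Specificity power: exact two-sided / asymptotic one-sided |
|---|---|---|---|---|
| 5% | 13 | 12% / 45% | 249 | 87% / 94% |
| 7.5% | 20 | 34% / 61% | 242 | 86% / 94% |
| 10% | 26 | 52% / 72% | 236 | 85% / 93% |

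Like for like at 7.5%, specificity power is 86 to 89% two-sided and 92 to 94% one-sided. By the normal approximation, 78% sensitivity power needs about 35 paired positive nodes (one-sided). For specificity, 99% needs about 385 (one-sided) or 450 (two-sided) paired negative nodes.

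**Step 4: sentinel node biopsy only.** The documents give no sentinel-node yield. Assuming 2 to 6 nodes per subject, there are 20 to 60 paired nodes (effective 19.9 to 58.5). At 7.5% prevalence, 1.5 to 4.4 are positive and exact sensitivity power is essentially zero. With four or fewer positive nodes a one-sided exact test cannot reach 0.05, since 0.5⁴ = 0.0625. Specificity power is 13 to 31% (two-sided, normal approximation). If prevalence among these nodes were 30% (also an assumption), giving 6 to 18 positive nodes, exact sensitivity power would be 0.3 to 28%.

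**Step 5: selective verification.** Cohort 1 nodes reach pathology mainly because they are radioactive. Among nodes with histology, Lymphoseek sensitivity is therefore pushed towards 1 and its specificity towards 0. More nodes of this kind would not make the contrast informative.

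**The case against.** The strongest reply is that section 12.1.3 never names Lymphoseek as the second test, so the mismatch is inferred. Other node-level readings exist: the surgeon's inspection for suspicious nodes in Cohort 2, and closed-field against open-field imaging of excised tissue. But the plan designates neither as a comparator, so neither supports the stated power, and leaving the pair unnamed is itself a defect.

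Some text also points the other way. Section 4.5 speaks of lymphadenectomy while mentioning Cohort 1 tracing, and section 12.1.3 counts dissections across all 20 subjects. The opening of section 2.4.2 mentions both agents without naming a cohort. These passages must be reconciled with Table 1 and sections 3.1 and 4.1. Step 3 already grants Cohort 1 a full dissection, and the stated power still fails.

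Three points stand in part. Section 2.4.3.3 allows for some excised nodes that are not radioactive, so values near 1 and near 0 are a tendency, not documented figures. Specificity power in the generous case remains fairly high, though below the claim. And the plan does call the study exploratory, concedes that power is limited and promises 95% confidence intervals. Even so, it claims excellent power for specificity and tests at the 0.05 level.

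**Conclusion.** The concern holds. The arithmetic is sound; the node base is not available. Under the most favourable reading of Cohort 1, across the plan's own 5 to 10% prevalence range, sensitivity power is 12 to 52% (exact) or 45 to 72% (asymptotic) against a stated 78%. Specificity power is 85 to 94% against a stated 99%. Neither claim is met in any of these cases.

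This rests on Lymphoseek being confined to Cohort 1, as Table 1 and sections 4.1 and 4.5 state, and on the plan's own ICC, discordance and effect sizes. The sentinel-node-only figures rest on assumed yields and are illustrative, but power must fall further as paired nodes become fewer.

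**What to change.** Amend the protocol wording; no added patients or procedures are needed.

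1. Give expected nodes by cohort: about 300 dissected nodes from Cohort 2 on the plan's inputs (15 necks × 20), plus the expected sentinel nodes from Cohort 1. Reconcile sections 2.4.2, 4.5 and 12.1.3 with Table 1 and sections 3.1 and 4.1.
2. Name the paired comparison, and make the synopsis and section 12.1.2 agree.
3. Withdraw both power claims and label the Lymphoseek comparison descriptive. Do not substitute a paired power on Cohort 1 nodes, for the reason in Step 5.
4. Justify 20 subjects by the expected precision of fluorescence sensitivity and specificity, with cluster-adjusted intervals. As an illustration, apply the pooled prevalence to 300 Cohort 2 nodes with one positive node missed. Exact 95% intervals before clustering are 68 to 99.8% (14/15, at 5%), 77 to 99.9% (21/22, at 7.5%) and 83 to 99.9% (29/30, at 10%). With 300 − 22 = 278 negative nodes, a specificity of 257/278 (92.4%) gives 89 to 95%. If more of the positive nodes fall in Cohort 2, the sensitivity intervals narrow.
5. State prevalence by cohort. Cohort 2 is entirely cN+, so the pooled rate need not apply. Section 12.1.3 also describes 10 subjects as having nodal metastasis yet expects metastatic nodes in only 6 to 8 of 20; say whether the first is clinical and the second histological.

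The cost is a less favourable-looking sample-size section and a Lymphoseek comparison that no longer carries a formal claim.

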APPENDIX A: Participant Eligibility Checklist

A Participant Eligibility Checklist will be completed in its entirety for each subject prior to registration. The completed, signed, and dated checklist will be retained in the subject's study file and the study's Regulatory Binder.

The study coordinator, treating physician and an independent reviewer will verify that the participant's eligibility is accurate, complete, and legible in source records. A description of the eligibility verification process should be included in the EPIC or other Electronic Medical Record progress note.

Protocol Title:	A Phase 2 Study Evaluating Panitumumab-IRDye800 vs. Sentinel Node Biopsy and (Selective) Neck Dissection for Metastatic Lymph Node Identification in Patients with Head and Neck Cancer
Protocol Number:	IRB-43013
Principal Investigator:	[name]

I. Subject Information:

Subject Name/ID:
Gender:  Male  Female

II. Study Information:

SRC-approved IRB-approved Contract signed

III. Inclusion/Exclusion Criteria

Inclusion Criteria (From IRB-approved protocol)	Yes	No	Supporting Documentation**
1. Biopsy confirmed diagnosis of squamous cell carcinoma of the head and neck			
2. Subjects with recurrent disease or new primary will be allowed			
3. Planned standard of care surgery with curative intent for squamous cell carcinoma			
4. *SNB only cohort: Subjects diagnosed with a T1-T2 stage tumor, any subsite within the head and neck that is amenable to local sentinel node tracer injection and are scheduled to undergo surgical resection of the tumor, including a sentinel node biopsy			
5. *Neck dissection only cohort: Subjects diagnosed with any T stage, any subsite within the head and neck that are scheduled to undergo surgical resection, including a (modified) neck dissection			

6. Age \geq 19 years			
7. Karnofsky performance status of at least 70% or ECOG/Zubrod level 1			
8. Have acceptable hematological status, coagulation status, kidney function, and liver function including the following clinical results: i. Hemoglobin \geq 9 gm/dL ii. White blood cell count $>$ 3000/mm ³ iii. Platelet count \geq 100,000/mm ³ iv. Serum creatinine \leq 1.5 times upper reference range			

*ONLY ONE CRITERION TO BE CHECKED FOR EACH PARTICIPANT - EITHER 4 or 5.

Exclusion Criteria (From IRB-approved protocol)	Yes	No	Supporting Documentation**
1. Myocardial infarction (MI); cerebrovascular accident (CVA); uncontrolled congestive heart failure (CHF); significant liver disease; or unstable angina within 6 months prior to enrollment			
2. History of infusion reactions to monoclonal antibody therapies			
3. Pregnant or breastfeeding			
4. Magnesium or potassium lower than the normal institutional values			
5. Subjects receiving Class IA (quinidine, procainamide) or Class III (dofetilide, amiodarone, sotalol) antiarrhythmic agents			
6. Subjects with a history or evidence of interstitial pneumonitis or pulmonary fibrosis			
7. Hypersensitivity to dextran and/or modified form thereof			

**All subject files must include supporting documentation to confirm subject eligibility. The method of confirmation can include, but is not limited to, laboratory test results, radiology test results, subject self-report, and medical record review.

IV. Statement of Eligibility

By signing this form of this trial I verify that this subject is [**eligible** / **ineligible**] for participation in the study. This study is approved by the Stanford Cancer Institute Scientific Review Committee, the Stanford IRB, and has finalized financial and contractual agreements as required by Stanford School of Medicine's Research Management Group.

Treating Physician Signature:	Date:
Printed Name:	

Secondary Reviewer Signature:	Date:
Printed Name:	

Study Coordinator Signature:	Date:
Printed Name:	

Appendix B – Imaging Devices Appendix

Device name	Manufacturer	Commercially available?	510(k)	Non-significant risk?	Serial No. of submission to [REDACTED]
Intraoperative near-infrared fluorescence imaging, in vivo					
Spy-Phi and/or PINPOINT– IR9000 (Handheld/Endoscopic)	Novadaq Inc.	Yes (modified light source for our study)	No	Yes	SN0008
Explorer Air	SurgVision	Yes (modified light source for our study)	No	Yes	SN0008
PDE-NEO II and/or FIGS	Hamamatsu Photonics K.K.	Yes	Yes	Yes	SN0012
IMAGE1 + ICG Hopkins telescope and/or VITOM	Karl Storz Endoscopes	Yes	Yes	N.A.	N.A.
Vevo LAZR-X	VisualSonics	Yes (for preclinical imaging)	No	Yes	In progress
Firefly for da Vinci	Intuitive Surgical Inc.	Yes	Yes	N.A.	N.A.
Intraoperative near-infrared fluorescence imaging, ex vivo (back table)					
Spy-Phi and/or PINPOINT– IR9000 (Handheld/Endoscopic)	Novadaq Inc.	Yes (modified light source for our study)	No	Yes	SN0008
Explorer Air	SurgVision	Yes (modified light source for our study)	No	Yes	SN0008
PDE-NEO II and/or FIGS	Hamamatsu Photonics K.K.	Yes	Yes	Yes	SN0012
IGP ELVIS v4	LI-COR Biosciences	No	No	Yes	SN0012
IMAGE1 + ICG Hopkins telescope and/or VITOM	Karl Storz Endoscopes	Yes	Yes	N.A.	N.A.
Vevo LAZR-X	VisualSonics	Yes (for preclinical imaging)	No	Yes	In progress
Firefly for da Vinci	Intuitive Surgical Inc.	Yes	Yes	N.A.	N.A.

Device name	Manufacturer	Commercially available?	510(k)	Non-significant risk?	Serial No. of submission to [REDACTED]
Laboratory near-infrared fluorescence imaging, ex vivo					
Pearl Trilogy	LI-COR Biosciences	Yes	N/A	N/A	N/A
Odyssey CLx	LI-COR Biosciences	Yes			
IGP ELVIS v4	LI-COR Biosciences	No			
Leica fluorescence microscope	Leica	Yes			
Vevo LAZR-X	VisualSonics	Yes			
Dosimeter	Pogue Laboratory	No			
Stand-alone Firefly for da Vinci	Intuitive Surgical Inc.	Yes, on the robot
